Blood sampling for LDL-C and PCSK9	X ^l	X ^l	X ^l (pre-dose and then 48 h post-dose)	X ^{l,m}	X ^{l, m} (pre-dose)	X ^{l, m}		X ^l (pre-dose and then 24 h post-dose)	X ^l	X ^m	
Blood sampling for other lipid parameters	X ^l	X ^l	X ^l (pre-dose and then 48 h post-dose)	X ^{l,m}	X ^{l, m} (pre-dose)	X ^{l, m}		X ^l (pre-dose and then 24 h post-dose)	X ^l	X ^l	

	Screening	Treatment Period							Follow-up Period		Corre-sponding Section in Protocol
		1	2	3	6	4, 5, 7, 8	9	10 to 16	17 (Final Follow-up Visit/ ED Visit)		
Visit Number	1	2	3	6	4, 5, 7, 8	9	10 to 16	17 (Final Follow-up Visit/ ED Visit)	Week 16 (after last dose)	Corre-sponding Section in Protocol	
Study Day/Week	Days -28 to -4	Day -1	Days 1 to 3	Day 8 ^a	Day 29	Days 15, 22, 36, 44	Day 56	Days 57 to 59	Weeks 2, 4, 6, 8, 10, 12, 14 (after last dose)	Week 16 (after last dose)	
Visit Window	-	-	-	-	± 1 day	± 1 day	± 1 day	± 1 day	± 2 days	± 2 days	
Exploratory biomarker sampling											
Plasma and urine samples to be stored in the Biobank until further analysis ⁱ			X (pre-dose)	X	X (pre-dose)			X (pre-dose)	X (Weeks 2 and 4 after last dose)	X	
Pharmacokinetic s											

	Screening	Treatment Period							Follow-up Period		Corre-sponding Section in Protocol
		Visit Number	1	2	3	6	4, 5, 7, 8	9	10 to 16	17 (Final Follow-up Visit/ ED Visit)	
Study Day/Week	Days -28 to -4	Day -1	Days 1 to 3	Day 8 ^a	Day 29	Days 15, 22, 36, 44	Day 56	Days 57 to 59	Weeks 2, 4, 6, 8, 10, 12, 14 (after last dose)	Week 16 (after last dose)	
Visit Window	-	-	-	-	± 1 day	± 1 day	± 1 day		± 2 days	± 2 days	
Plasma for AZD8233 and total full length ASOs of AZD8233 ^j			X (pre-dose and then 0.5, 1, 1.5, 2, 2.5, 3, 4, 5, 6, 8, 10, 12, 24, 36 and 48 h post dose)	X	X (pre-dose)	X		X (pre-dose and then 0.5, 1, 1.5, 2, 2.5, 3, 4, 5, 6, 8, 10, 12, 24, 36 and 48 h post dose)	X	X	Section 8.5.1
Urine for total full length ASOs of AZD8233			X (pre-dose and intervals 0-6, 6-12, 12-24 h post-dose)					X (pre-dose and intervals 0-6, 6-12, 12-24 h post-dose)			Section 8.5.1

ASO: Antisense oligonucleotides; BMI = body mass index; ET = early termination; FSH = follicle-stimulating hormone; hs-CRP = high sensitive C-reactive protein; IMP: Investigational medicinal product; LDL-C = low-density lipoprotein cholesterol; LH = luteinizing hormone; PCSK9 = proprotein convertase subtilisin/kexin type-9; SAE: Serious adverse event

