On Day -1, eligibility criteria must be verified by checking screening labs and inclusion/exclusion criteria. An abbreviated physical examination must be performed. Blood and urine samples will be obtained prior to administration of study intervention in fasted state. Vital signs and BMI will be checked. Cardiac telemetry should be performed for at least 4 hours.

On Day 1, he/she will be randomized in IXRS, and the study intervention will be administered

as an SC injection.

An abbreviated physical examination must be performed. Blood and urine samples will be obtained prior to administration of study intervention in fasted state. An ADA sample will be obtained pre-dose. Vital signs, ECG, and cardiac telemetry will be performed.

On Day 3, the participant will be discharged after the results from the 48 hours post-dose assessments have been reviewed by the Principal Investigator.

Visits 3 and 6 (Part A:treatment visit): Visit 3 (Day 8) and Visit 6 (Day 29 ± 1 day) are planned as clinical visits. At Visit 3 and Visit 6, the study intervention will be administered as an SC injection. Blood sampling for LDL-C, PCSK9, and other lipid parameters should be taken in the morning after a 10-hour fast. No fluids will be allowed apart from water, which can be given until 1 hour before blood sampling for LDL-C, PCSK9, and other lipid parameters. Blood and urine sampling must be performed prior to administration of study intervention. PK sampling must be done pre-dose. An abbreviated physical examination, ECG, and vital signs examination must be performed prior to administration of study intervention. At Visit 6, the ADA sampling must be done pre-dose.

Visits 3 (Part C:non-treatment visit): Visit 3 (Day 8) is planned as clinical visits. Blood sampling for LDL-C, PCSK9, and other lipid parameters should be taken in the morning after a 10-hour fast. No fluids will be allowed apart from water, which can be given until 1 hour before blood sampling for LDL-C, PCSK9, and other lipid parameters. Blood and urine sampling must be performed. PK sampling must be done. An abbreviated physical examination, ECG, and vital signs examination must be performed.

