Visits 6 (Part C:treatment visit): Visit 6 (Day 29 ± 1 day) is planned as clinical visits. At Visit 6, the study intervention will be administered as an SC injection. Blood sampling for LDL-C, PCSK9, and other lipid parameters should be taken in the morning after a 10-hour fast. No fluids will be allowed apart from water, which can be given until 1 hour before blood sampling for LDL-C, PCSK9, and other lipid parameters. Blood and urine sampling must be performed prior to administration of study intervention. PK sampling must be done pre-dose. An abbreviated physical examination, ECG, and vital signs examination must be performed prior to administration of study intervention. The ADA sampling must be done pre-dose.

Visits 4, 5, 7, and 8 (non-treatment visit): Visit 4 (Day 15 ± 1 day), Visit 5 (Day 22 ± 1 day), Visit 7 (Day 36 ± 1 day), and Visit 8 (Day 44 ± 1 day) are planned as clinical visits. At Visit 5 and Visit 8, blood sampling for platelet count must be done. Blood sampling for LDL-C, PCSK9, and other lipid parameters should be taken in the morning after a 10-hour fast. No fluids will be allowed apart from water, which can be given until 1 hour before blood sampling for LDL-C, PCSK9 and other lipid parameters. PK sampling must be done.

Visit 9 (treatment visit): Visit 9 (Days 56-59; \pm 1 day) is planned for hospitalization. Participants should be admitted on Day 56 and will be discharged after the results from the 48 h post-dose assessments have been reviewed by the Principal Investigator.

On Day 56, blood sampling for platelet count must be done.

On Day 57, the study intervention will be administered as an SC injection. Weight will be checked. ADA, blood, and urine sampling must be performed prior to administration of study intervention. Blood sampling for LDL-C, PCSK9, and other lipid parameters should be taken in the morning after a 10-hour fasting. No fluids will be allowed apart from water, which can be given until 1 hour before blood sampling for LDL-C, PCSK9, and other lipid parameters. Vital signs, ECG, and cardiac telemetry to be performed. An abbreviated physical examination must be performed 24 hours post-dose. PK sampling must be done.

Follow-up contact (Part A: Day 64 + 2 days): One telephone contact from a participant's site (or an investigator) to assess AEs.

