Follow-up visits (Visits 10-16): At all follow-up visits, ECG and an abbreviated physical examination are required, and vital signs, blood, and urine samples are to be checked.

An ADA sampling is to be performed at Visit 10 (Week 2 after last dose; \pm 2 days). At all follow-up visit PK sampling is to be performed.

Early Discontinuation Visit: The EDV may take place any time during the study, in case a participant discontinues study treatment prior to Visit 9 (where last dose of study treatment is administered). The same assessments as done during the final follow-up visit will be performed. See Section 7.1.

Final follow-up visit (Visit 17): The final follow-up visit will be performed in Week 16 after last dose (\pm 2 days). PK and ADA sampling is to be performed. A complete physical examination must be performed on the visit, and body weight, BMI, vital signs, body temperature, and ECG are to be checked. Blood and urine sampling is to be obtained.

The maximum blood volume to be drawn from each participant will not exceed 800 mL over the duration of the study period. Repeat or unscheduled samples may be taken for safety reasons or for technical issues with the samples.

[Part B]

Visit 1 (enrollment) and Visit 2: At Visit 1 (Day -28 to Day -10), participants will be asked to sign the informed consent and optional informed consent for future genetic research sample. Participant demographics and medical history, including smoking and alcohol consumption history, will be recorded in the eCRF. A complete physical examination must be

performed. Vital signs, height, weight, BMI, and ECG must be checked, as well as blood and urine sample collection. Visit 2 (Day -7 to Day -4) will include an additional blood sample collection for LDL-C, PCSK9, and triglycerides.

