4.2.5 Secondary Endpoint - Pharmacokinetics

4.2.5.1 Definition

Where possible, the following PK parameters will be determined.

AUC_{inf}	Area under the plasma concentration-time curve from time zero extrapolated to infinity. AUC is estimated by $AUC(0\text{-last}) + \text{Clast}/\lambda z$ where Clast is the last observed quantifiable concentration.
$AUC_{(0\text{-last})}$	Area under the plasma concentration-curve from time zero to the time of last quantifiable analyte concentration.
$AUC_{(0\text{-}24)}$	Area under the concentration-time curve from time zero to 24 hours post-dose.
$AUC_{(0\text{-}48)}$	Area under the concentration-time curve from time zero to 48 hours post-dose.
$AUC\tau$	Area under the plasma concentration-time curve during the dosing interval
CL/F	Apparent total body clearance of drug from plasma after extravascular administration.
C_{max}	Maximum observed plasma concentration.
C_{trough}	Observed trough plasma concentration
λz	Terminal rate constant, estimated by log-linear least-squares regression of the terminal part of the concentration-time curve.
MRT	Mean residence time of the unchanged drug in the systemic circulation.
$RAC(AUC)$	Accumulation ratio based on AUC
$RAC(AUC)(0\text{-}48)$	Accumulation ratio based on AUC from time zero to 24 hours post dose
$RAC(AUC)(0\text{-}168)$	Accumulation ratio based on AUC from time zero to 168 hours post dose
$RAC(C_{\text{max}})$	Accumulation ratio based on C_{max}
$t_{1/2z}$	Half-life associated with the terminal slope (λz) of a semi-logarithmic concentration-time curve
t_{lag}	Time delay between drug administration and the first observed concentration in plasma
t_{last}	Time of last quantifiable concentration.
t_{max}	Time to reach peak or maximum observed concentration following drug
Vz/F	Apparent volume of distribution during the terminal phase after extravascular administration.

The following PK parameters will be determined, where possible, from urine concentrations.

$Ae_{(t1\text{-}t2)}$	Amount of analyte excreted unchanged in urine from time $t1$ to $t2$
$fe_{(t1\text{-}t2)}$	Percentage of analyte excreted unchanged in urine from $t1$ to $t2$

$Ae_{(0\text{-last})}$	Cumulative amount of analyte excreted at the last sampling interval
$fe_{(0\text{-last})}$	Cumulative percentage of dose excreted unchanged into the urine from time zero to the last measured time point for an analyte, estimated by dividing $Ae(0\text{-last})$ by dose

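### Part C PK: RAC(AUC)(0-48) is defined with a 24-hour AUC, and RAC(AUC)(0-168) has no sample near 168 h after the Day 57 dose

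*SAP*

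**What the plan says.** The Part C SAP, section 4.2.5.1, opens its parameter list with "Where possible, the following PK parameters will be determined". Among the accumulation ratios are two that are tied to a time window:

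- RAC(AUC)(0-48), described as "Accumulation ratio based on AUC from time zero to 24 hours post dose".
- RAC(AUC)(0-168), described as "Accumulation ratio based on AUC from time zero to 168 hours post dose".

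AUC(0-24) and AUC(0-48) are listed as separate parameters in the same table; AUC(0-168) is not. Neither row says which dose day is the numerator and which the denominator. Section 4.2.5.4 computes AUC by linear trapezoids when concentrations rise and logarithmic trapezoids when they fall.

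The Part C schedule (protocol section 1.3, Table 3) takes plasma pre-dose and at "0.5, 1, 1.5, 2, 2.5, 3, 4, 5, 6, 8, 10, 12, 24, 36 and 48 h post dose" on Days 1-3 and again on Days 57-59. Day 29 is sampled pre-dose only. Single samples are taken on Days 8, 15, 22, 36 and 44. In section 8 of the protocol, "Visit 3 (Day 8) is planned as clinical visits" for Part C, with a PK sample and no dose. After Day 57, "At all follow-up visit PK sampling is to be performed", and the first of these visits is two weeks after the last dose, with a window of 2 days either side. The only Day 64 contact is for Part A and is by telephone: "Follow-up contact (Part A: Day 64 + 2 days): One telephone contact".

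**The concern.** There are two separate problems.

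First, a programmer who follows the label and one who follows the definition of RAC(AUC)(0-48) will report different quantities, and each can claim to comply with the SAP. The next row's label and definition agree, so the mismatch does not look like an extraction fault.

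Second, the 0-168 h ratio compares two areas that rest on different sampling. On Day 1 the area is tied down by an observation at 168 h. On Day 57 the value at 168 h has to be read off a line drawn from 48 h to Week 2. If concentrations are still falling in more than one phase after 48 h, that line lies above the curve. The reported ratio can then show more accumulation than occurred, and nothing in the SAP would mark the value as interpolated. The rule for a missing Day 57 sample covers AUC over the dosing interval only.

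**Working it through.** **Label against definition.** The label says 0-48 h and the definition says 24 h. Both profiles have samples at 24 h and at 48 h, so either window can be computed on both days. The row alone does not settle which was meant.

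**Sampling in nominal hours.** Hours after dose = (visit day − dose day) × 24.

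| Dose | Visit | Hours | Part C plasma sample |
|---|---|---|---|
| Day 1 | Day 3 | 48 | yes |
| Day 1 | Day 8 | 168 | yes |
| Day 1 | Day 15 | 336 | yes |
| Day 57 | Day 59 | 48 | yes |
| Day 57 | Day 64 | 168 | no visit |
| Day 57 | Day 71 (Week 2) | 336 (288 to 384 with the window) | yes |

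Days 1 and 57 are the only doses with a full profile, so Day 57 over Day 1 is the natural reading of the ratio.

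**Direction of the bias.** For falling concentrations the SAP's rule gives

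AUC(t1,t2) = (C1 − C2)(t2 − t1) / ln(C1/C2).

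With one decay phase this is exact and there is no bias. With two phases the log curve is convex, so a chord lies above it, and a longer chord lies further above.

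**One worked case, AUC(48-168) only.** Take the same true curve on both days. The terminal half-life is 14 days, the lower end of the 2 to 3 weeks in protocol section 4.2. The fast half-life of 24 h and the fast-to-slow ratio of 3 at 48 h are assumed.

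- C(48) = 3 + 1 = 4
- C(168) = 3 × 2^(−120/24) + 2^(−120/336) = 0.0938 + 0.7807 = 0.8745
- C(336) = 3 × 2^(−288/24) + 2^(−288/336) = 0.0007 + 0.5520 = 0.5528
- With a 168 h sample (Day 1 pattern): (4 − 0.8745) × 120 / ln(4/0.8745) = 246.7
- Without it (Day 57 pattern): k = ln(4/0.5528)/288 = 0.00687 per h; the interpolated C(168) = 4 × exp(−120k) = 1.754; the area = (4 − 1.754)/k = 326.9
- True area: 206.9

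The two patterns differ by 326.9/246.7 = 1.325 on an identical curve. Day 1 is also too high (246.7 against 206.9), but by less. Over fast half-lives of 12-48 h, fast-to-slow ratios of 1-10 and terminal half-lives of 14-21 days, this segment ratio runs from 1.10 to 1.64.

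**Full 0-168 h ratio.** The effect is smaller here because 0-48 h is sampled identically on both days. The illustration uses a bi-exponential curve with first-order input, terminal half-life 14-21 days, and assumed values for the rest: distribution half-life 6-36 h, initial-to-terminal ratio 100-1000, absorption rate 0.3-1.0 per h.

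| Week 2 sample at | Upward bias in RAC(AUC)(0-168) |
|---|---|
| 288 h | about 1-14% |
| 336 h | about 1-18% |
| 384 h | up to about 22% |

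The true ratio in these cases is 1.00-1.12. In the worst case at 336 h a true ratio of about 1.03 comes out at about 1.21 (1.21/1.03 = 1.17). The bias was upward in every case tried.

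**The case against.** The strongest reply is that little hangs on this. The list is qualified by where possible, so an unsupported ratio need not be reported. The protocol's PK endpoint list for Parts A and C contains no accumulation ratio. The analysis is descriptive, with about eight participants on active drug, and no rule uses the ratio. All of that stands and keeps the point minor. The qualifier does not, however, stop software from returning an interpolated number with no flag.

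The size of the bias can also be challenged. Only the terminal half-life is documented. With an input half-life of 1 h, a distribution half-life of 6 h gives only 1.3-1.8%; values above 10% need roughly 12-24 h; at 36 h the bias falls back to 2-10%. The documents do not say which applies.

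AUC over the Day 57 dosing interval crosses the same gap, so deleting only the 0-168 h ratio is not a full principle. This is fair, and it makes a flag a reasonable alternative to deletion.

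Three stronger readings are tempting, and the documents do not support them:

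- A reader might infer that measuring accumulation on the Phase 3 regimen is a stated purpose of Part C. The protocol says only that Part C also investigates PK and PD, and section 4.3 ties the Phase 3 dose to LDL-C reduction and tolerability.
- A reader might infer that the Day 1 area is measured and the Day 57 area is not. Between 48 h and 168 h both are log chords; only the end point on Day 1 is observed.
- A reader might infer that the ratio cannot be calculated. It can, by interpolation; what is missing is an observation near 168 h.

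**Conclusion.** The point holds as a minor correction to the Part C SAP. The conflict between label and definition is on the face of section 4.2.5.1 and needs no assumption. The gap after Day 57, from 48 h to 336 h nominally and to 288 h at the earliest, follows directly from the schedule.

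The upward bias rests on two conditions: that the ratio is Day 57 over Day 1, and that decline after 48 h is multi-phase. Its size, about 1-18% at 336 h, is an illustration under assumed distribution-phase values and should not be read as an estimate for this drug. No primary result, safety conclusion or dose decision depends on it.

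**What to change.** In the Part C SAP, section 4.2.5.1:

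1. Reconcile the RAC(AUC)(0-48) row. The label points to 48 h, AUC(0-48) is already a listed parameter, and both profiles reach 48 h, so the natural wording is AUC(0-48) on Day 57 divided by AUC(0-48) on Day 1. Because AUC(0-24) is listed too, the sponsor should confirm that 24 was the slip.
2. State the numerator and denominator day for every accumulation ratio.
3. Delete RAC(AUC)(0-168), or keep it with a flag in tables and listings that the Day 57 area is interpolated from 48 h to Week 2 and has no observation near 168 h.
4. Describe accumulation with RAC(AUC)(0-48), RAC(Cmax) and the Ctrough values, which are already listed and sampled, including pre-dose on Days 29 and 57.

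The cost is a few lines of SAP text and, at most, one descriptive ratio. No new sample or visit is needed.

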4.2.5.2 Derivations

The geometric mean is calculated as the exponential of the arithmetic mean calculated from the data on the natural log scale.

The percent coefficient of variation is calculated as: $CV (\%) = \sqrt{(\exp(s^2) - 1)}$ where s is the standard deviation of the data on a log scale.

Handling of values below the lower limit of quantification (BLQ)

Plasma concentrations below the limit of quantification (BLQ) from the time of pre dose sampling ($t = 0$) up to the time of the first quantifiable concentration will be set to a value of 0. After the first quantifiable concentration, BLQ plasma concentrations will be set to missing for the calculation of PK parameters unless it is considered to be a true characteristic of the profile of the drug.

If two or more consecutive BLQ concentrations are followed by quantifiable concentrations in the terminal portion of the concentration curve, the profile will be deemed to have terminated and therefore these quantifiable values will be set to missing for the calculation of the PK parameters unless there is a scientific rationale not to do so, which will be documented in the CSR.

Any embedded BLQ value (between two quantifiable concentrations) will be set to missing for the PK analysis.

If an entire concentration-time profile is BLQ, the profile is excluded from the PK analysis.

For descriptive statistics plasma concentrations that are below the LLOQ will be handled as follows:

- At a time point where less than or equal to 50% of the values are BLQ, all BLQ values will be set to LLOQ, and all descriptive statistics will be calculated.

- At a time point where more than half of the values are BLQ, the mean, SD, geometric mean and CV% will be set to Not Determined (ND). The max value will be reported from the individual data, and the min and median will be set to BLQ.
- If all values are BLQ at a time point, no descriptive statistics will be calculated for that time point. Not applicable (NA) will be written in the field for SD and CV% and BLQ will be written in fields for mean, geometric mean, min, median, and max.
- The number of BLQ values (n below LLOQ) will be reported for each time point.
- Where there is no result, these will be set to missing.

Urine concentrations that are below the LLOQ will be handled as follows:

- BLQ values should be set to zero for the calculation of individual Ae.
- Any resulting Ae values equal to zero should be set to missing for the calculation of the summary statistics.

4.2.5.3 Handling of Dropouts and Missing Data

Not applicable

4.2.5.4 Primary Analysis of Secondary Endpoint

A listing of PK blood sample collection times as well as derived sampling time deviations will be provided. A listing of urine sample collection start and stop times will be provided. Urine amount and fraction of dose excreted (by interval and cumulative) will be listed.

Pharmacokinetic Concentrations

Plasma concentrations, amount excreted in urine (Ae), and fraction of dose excreted (per collection interval and cumulative) and PK parameters will be summarized by analytes and timepoints using descriptive statistic, number of non-missing observations, n below LLOQ, arithmetic mean, SD, geometric mean, geometric coefficient of variation (CV%), min, median, max and based upon the PK analysis set.

Where the actual time that a sample was taken deviates by more than the specified time allowances from the nominal time then concentration will be excluded from the summary statistics and statistical analysis.

Nominal Time	Time allowance
Pre-dose	Up to 30 minutes prior to dosing
0.5 h post dose	± 2 minutes
1 h post dose	± 5 minutes

1.5 h post dose	± 5 minutes
2 h post dose	± 5 minutes
2.5 h post dose	± 5 minutes
3 h post dose	± 10 minutes
4 h post dose	± 10 minutes
5 h post dose	± 10 minutes
6 h post dose	± 10 minutes
8 h post dose	± 10 minutes
10 h post dose	± 30 minutes
12 h post dose	± 30 minutes
24 h post dose	± 1 hour
36 h post dose	± 1 hour
48 h post dose	± 1 hour

Data from subjects excluded from the PK population will be included in the data listings, but not in the summaries or in the inferential statistics.

For t_{max} and time of last quantifiable plasma concentration (t_{last}) only n, median, minimum and maximum will be used.

Pharmacokinetic parameters will be rounded for reporting purposes in the summary tables and subject listings, as per the PK order form provided by AZ.

Individual plasma concentrations versus actual time will be plotted by analyte in linear and semi-logarithmic scale, with separate plots for each subject and study day. Plots will be based on the PK analysis set and displayed up to 48 hours post-dose.

Combined individual plasma concentration versus actual times will be plotted by analyte and study day in linear and semilogarithmic scale. Plots will be grouped by dose level, based on the PK analysis set and displayed up to 48 hours post-dose.

Figures for the arithmetic mean concentration-time data will be presented for all groups (pool data from all treatment groups) overlaid on the same plot, in both a linear and semi-logarithmic scale (SD on the linear scale and gSD on the semi-logarithmic scale) with separate plots for each study day.

Additional graphical presentations of PK data may be added at the discretion of the PK scientist.

Pharmacokinetic data will be presented by analytes and timepoints. A listing of all concentration-time data will be presented by dose level.

The following rules will be followed with regards to the number of decimal places and presentation of data in the tables and listings of concentration data:

1. Source data shall be used in all derived PK concentrations without prior rounding.
2. The mean, standard deviation, geometric mean and median will be tabulated to one more significant digit compared to the source data, but with a maximum of four significant digits.
3. Minimum and maximum values will be tabulated to the same precision as the source data, but with a maximum of four significant digits.
4. Geometric coefficient of variation and coefficient of variation will be presented to one decimal place.

Graphical Presentation

For individual figures, concentrations that are BLQ will be regarded as missing, with the exception of pre-dose BLQ values which will be set to zero for linear scale plots.

For mean plots, BLQ values will be handled as described for the summary tabulations so that the same plasma concentration values are used in the mean data graphs as those given in the descriptive statistics summary table for each time point. All mean plots will be based on the PK analysis set.

Pharmacokinetic Parameters

Pharmacokinetic parameters will be derived using noncompartmental methods with WinNonlin® Professional Version 8.3, or higher, (Certara) and/or SAS® Version 9.3, or higher (SAS Institute, Inc., Cary, North Carolina). All descriptive and inferential statistical computations will be performed using SAS® Version 9.3, or higher.

The actual sampling times, recorded in the raw data, will be used in the final plasma PK parameter calculations. If actual times are missing, nominal times may be used.

Nominal sampling times will be used for interim plasma PK parameter calculations.

Nominal times will be used for the calculation of urine PK parameters.

Concentration data will be used as supplied by the analytical laboratory for PK analysis. The units of concentration and resulting PK parameters, with amount and concentration units, will be presented as they are received from the analytical laboratory.

Dose normalized parameters for AUC_{last} , AUC and C_{max} will be calculated by dividing the original parameter by dose.

The C_{max} and time to reach peak or maximum observed concentration or response following drug administration (t_{max}) will be derived directly from the plasma concentration-time profiles. For multiple peaks the highest post dose concentration will be reported as C_{max} . In the case that the multiple peaks are of equal magnitude, the earliest t_{max} will be reported.

Terminal elimination half-life, estimated as $(\ln 2)/\lambda_z$, where λ_z refers to the terminal elimination rate constant, will be estimated by log linear least squares regression of the terminal part of the concentration-time curve.

The choice of data points used to estimate λ_z should follow the general guidelines:

- If there is more than 1 phase, use only observations from the terminal phase.
- In general, the minimum data requirements are 3 measured concentrations spanning three half-lives. Where $t_{1/2}$ is estimated over less than three half-lives, the values will be flagged in the data listings.
- Should include the last measurable concentration.
- Include only observations after C_{max} .
- The adjusted correlation coefficient (regression coefficient adjusted for λ_z , N, goodness of fit statistic for calculation of λ_z ; R^2 adj) should be ≥ 0.8 .

Area under the plasma concentration-curve will be calculated using trapezoidal methods when concentration is increasing and logarithmic trapezoidal method when concentrations are decreasing (linear up log down).

Three concentrations higher than the LLOQ are required as a minimum for the AUC parameter to be calculated.

If the pre-dose concentration prior to the first dose is missing it will be set to zero by default. If the pre-dose sample on Day 57 is missing it may be set equal to the concentration at the end of the dosing interval for the calculation of area under the plasma concentration-time curve in the dosing interval ($AUC\tau$) assuming linear PK and steady state conditions apply.

If the sample at the end of the profile is missing on Day 57 the concentration may be set equal to the pre-dose value for the calculation of $AUC\tau$ assuming linear PK and steady state conditions apply.

If a plasma or urine concentration value is considered anomalous due to being inconsistent with the expected pharmaceutical profile it may be appropriate to exclude this data point from the PK analysis. However, the exclusion of any data must have strong justification and will be documented in the study report. Embedded BLQs may be considered anomalous depending on the characteristics of the drug.

Urine PK parameters will be calculated based on measurements with the ECL assay. In case of an incomplete urine collection in any of the specified collection intervals (eg, spilled sample), the calculation of the fraction of dose excreted into urine as well as renal clearance will be subject to discretion of the AZ study pharmacokineticist.

The amount excreted in urine (A_e) will be calculated using a urine density of 1.0 g/mL. Urine concentrations below LLOQ will be treated as numerical zero.

The amount of analyte excreted into the urine from time t_1 to t_2 [$A_e(t_1-t_2)$] and percentage excreted unchanged in urine from t_1 to t_2 [$f_e(t_1-t_2)$] will be calculated by collection interval and cumulatively for all collection intervals.

